11.3.3. Secondary Analyses

For efficacy/performance, bone consolidation will be assessed by 12 months as measured by Investigator assessment. For Safety, the incidence of device-related adverse events/incidents by 12 months will be monitored through collection and analyses. Both analyses will be part of the annual and final reports.

Furthermore, device related adverse events/incidents and the time to (earliest) Device Related Adverse Events/incidents will be analyzed as well. Considered variables, the level of measurement and the planned analysis steps are listed in detail in the SAP.

11.3.4. Additional Analyses

Additional Analyses are outlined in the subsequent sections. Analysis details (variables, level of measurement, planned steps) are listed in-depth in the SAP.

Weight-bearing status

The weight bearing status will be evaluated and analyzed at the pre-operative visit and at 3 months, 6 months and 12 months. The within subject changes from visit to visit will be analyzed in addition. This analysis will be part of the annual and final reports.

External Support

The status of the subject using external support will be evaluated at the pre-operative visit and at 3 months, 6 months and 12 months. The within subject changes from visit to visit will be analyzed in addition. This analysis will be part of the annual and final reports.

Mortality

For analysis of the time to death or mortality, the Kaplan-Meier method will be used. The times between the date of surgery and the date of the 12 months assessment will be used together with the times between surgery and the date of death. This analysis will be part of the annual and final reports.

Reoperation

For analysis of the time to the reoperation, the Kaplan-Meier method will be used. The times between the date of surgery and the date of the 12 months assessment will be used together with the times between date of surgery and the date of reoperation (earliest reoperation in case that one subject experienced more than one reoperation). This analysis will be part of the annual and final reports.

SF-36 Total Score – Within subject changes by visit

The within subject score changes of the SF-36 Total Score from visit to visit will be analyzed to help identify the changes on the subject level. This analysis will be part of the annual and final reports.

11.4. MISSING DATA / SAP DEVIATIONS

The intent is to collect as complete a dataset as possible. Nevertheless, in some situations missing data cannot be avoided. The reports and tables therefore will show the number and percentage of missing cases for each analyzed variable in relation to the enrolled cases for each post-operative assessment

Any deviations from Statistical Analysis Plan will be listed in the annual or final reports.

11.5. REPORTS

11.5.1. Interim Analysis and Reports

Interim analyses will be performed on a yearly basis. The progress of the clinical investigation will be reported together with the interim results on the variable level according to the analysis plan. The only exception is the analysis of the primary endpoint will not be part of the interim reports.

11.5.2. Final Analysis and Reports

The full final report with complete analysis and progress and conduct reporting will be created at the end of this clinical investigation.

12. Clinical Investigation Plan Deviations

A Clinical Investigation Plan (CIP) deviation is a departure from the approved CIP that is not implemented or intended as a systemic change. All CIP deviations are recorded and reported to each site's IRB/EC in accordance with the respective site's IRB/EC policies.

13. Adverse Events/Incidents

As this CIP is being carried out to satisfy the post-market requirements to support safety and efficacy/performance according to the Council Directive 93/42/EEC concerning medical devices (Annex X (1.1c)) (MDD 93/42/EEC) and Regulation 2017/745 on medical (MDR 2017/745), categorization and definition of device related adverse events will follow the guidelines outlined in the MDR 2017/745 as "incident" reporting. The following AE terminology will apply:

An Adverse Device Effect (ADE) is defined as any untoward or unintended response to the clinical investigation treatment; and/or a medical response which may have a causal relationship to the treatment.

- An Incident is defined as any malfunction or deterioration in the characteristics or performance of a device made available on the market, including use-error due to ergonomic features, as well as any inadequacy in the information supplied by the manufacturer and any undesirable side-effect.
- A Serious Adverse Device Effect (SADE) is defined as any ADE that results in consequences characteristic of a SAE or might lead to the consequences if suitable action or intervention is not taken; causes considerable interference with the subject's usual activities and may be incapacitating or life-threatening, including those events resulting in a subject's disability or permanent damage, or required intervention to prevent disability or permanent damage; results in a life-threatening illness or injury; and/or results in death (fatal).
- A Serious Incident is defined as any incident that directly or indirectly led, might have led or might lead to any of the following:
 - o the death of a patient, user or other person;
 - o the temporary or permanent serious deterioration of a patient's, user's or other person's state of health;
 - o a serious public health threat
- An Unanticipated Adverse Device Effect (UADE) is defined as an Adverse Event not described in the informed consent, Clinical Investigation Plan or device labeling which has resulted in any of the

. .

consequences of a SAE or which might have led to any of the consequences of a SAE if suitable action had not been taken, intervention had not occurred, or if circumstances had been less opportune. Anticipated Adverse Events will be those listed in the T2 Alpha Tibia Nailing System device labeling (Operative Technical Manual and Instructions for Use).

13.1. ADVERSE EVENT/INCIDENT SEVERITY

The severity of all AEs/incidents is assessed by the Investigator utilizing the following categories:

- **Mild:** The AE/incident is transient and easily tolerated by the subject.
- **Moderate:** The AE/incident causes the subject discomfort and interrupts the subject's usual activities.
- **Severe:** The AE/incident causes considerable interference with the subject's usual activities and may be incapacitating or life-threatening. This includes those events that result in a subject's disability or permanent damage, and/or required intervention to prevent permanent disability or damage.
- Life-threatening: The AE/incident results in a life-threatening illness or injury.
- **Fatal:** The AE/incident results in death.

13.2. RELATIONSHIP TO THE DEVICE

Only adverse events/incidents that are considered possibly, probably or definitely related to the device will be captured for this clinical investigation.

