3.3. EDC SYSTEM

Name: IBM Clinical Development Email: [contact] [contact]

4. Product Information

All components of the T2 Alpha Tibia Nailing System were cleared and approved for sale and use prior to starting the clinical investigation. 510(k) clearance was received on 06Jun2018. This system is to be used only for indications for which it has been approved. Please see the approved Instructions for Use and Operative Technique manuals for a detailed description of the medical device(s) and instrumentation, and intended use information.

Medical device product traceability will be achieved by capturing the implant lot number.

5. Risks and Benefits

This prospective, multi-center, clinical investigation is designed to examine the safety and efficacy/performance of the T2 Alpha Tibia Nailing System, in accordance with the approved instructions for use, labeling and instrumentation. The potential risks to subjects are described in the approved Instructions for Use and Operative Technique manuals.

Potential benefits resulting from the T2 Alpha Tibia Nailing System over other devices and procedures, as demonstrated by superior scoring on outcome surveys and positive results on other clinical evaluation measurements (outlined in section 8), would also suggest affirmative clinical efficacy.

6. Introduction

The T2 Tibia Nailing System represented the latest and most comprehensive development of the original intramedullary principles presented by [name] in 1940. As an addition to the T2 Nailing System, Stryker has created a new generation tibial implant that offers an efficient treatment option for multiple indications. The T2 Alpha Tibia Nail includes new locking options and the ability to utilize the advanced locking screw which creates an axial and angular stable construct. New instrumentation offers a combination of innovation, simplicity and efficiency that is designed to suit the various needs of surgeons and OR staff.

7. Clinical Investigation Design

This investigation is a prospective, multicenter clinical investigation. It is anticipated that a total of 80 subjects will be enrolled at up to 5 sites. Enrollment is estimated to commence in Q4 of 2018. Neither

. .

subjects nor investigators are blinded to treatment and the clinical investigation includes a historical control which will be compared to the T2 Alpha Tibia Nailing System.

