8.2. SECONDARY ENDPOINTS

- Safety: Incidence of device-related adverse events by 12 months will be monitored through collection and analyses.
- Efficacy/Performance: Bone consolidation will be assessed by 12 months as measured by Investigator assessment.

9. Selection of Clinical Investigation Population

Subjects participating in this clinical investigation will be recruited from the investigator's standard subject population, where all subjects presenting for treatment of tibial fractures will be evaluated for clinical investigation participation based on the eligibility criteria listed below.

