13.3. FORESEEABLE ADE AND SADE

ADEs, SADEs and incidents which may be expected as part of the surgical interventions include:

- Axial malalignment
- Chondromalacia
- Compartment syndrome
- Deep vein thrombosis
- Delayed union
- Fat embolism
- Hematoma
- Iatrogenic fracture
- Implant breakage (nail)
- Implant breakage (screw)
- Implant failure (nail)
- Implant failure (screw)
- Implant loosening (nail)
- Implant loosening (screw)
- Infection (deep)
- Infection (superficial)
- Malunion

- Necrosis
- Non-union
- Pain
- Peripheral nerve injury without specification
- Pressure ulcer
- Pre-tibial fistula
- Pulmonary embolism
- Rotational malalignment

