13.4. ADVERSE DEVICE EFFECT/INCIDENT REPORTING AND ANALYSIS

In the event that a SADE, UADE or serious incident occurs, the Investigator is required to notify the Sponsor within 48 hours of being made aware of the event. The Investigator is also required to notify their IRB/EC in accordance with the policies of their local laws and regulations.

14. Reoperations

Reoperations and reason(s) for reoperations will be collected throughout the course of the clinical investigation. A reoperation may include, but not limited to, irrigation and debridement, revision surgery, and/or implant removal.

15. Ethics

This clinical investigation is to be conducted according to International Conference of Harmonisation of Good Clinical Practice (ICH-GCP), applicable regulations, institutional research policies and procedures, Declaration of Helsinki and in compliance with the Clinical Investigation Plan (CIP). Investigators will be trained on the clinical investigation devices and surgical techniques prior to implanting clinical investigation subjects.

This CIP and any amendments will be submitted to a properly constituted independent ethics board, in agreement with local legal prescriptions, for formal approval of the clinical investigation conduct. The decision of the ethics board concerning the conduct of the clinical investigation will be made in writing to the Site Principal Investigator before commencement of this clinical investigation. Clinical investigations shall not begin until the governing regulatory authority has provided full, unconditional approval. Off-label use of the T2 Alpha Tibia Nailing System is not permitted.

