Type of Procedure (Variable(s): TOPAMP; TOPDYNA; TOPIMPREM; TOPIRDEB; TOPRTAINTFIX; TOPINTSPF; TOPREVARTH; TOPARTHSPF; TOPRTAEXTFIX; TOPEXTSPF; TOPOTH; TOPOTHSPF)	Qualitative, nominal	Proportions, frequencies, column and row totals, missing proportion (if any). Listings of implant specifications.	Х	Х	
Reason(s) for Reoperation (Variable(s): DELUNION; IATRFRAC; IMPBRAK; IMPLFAIL; IMPLOOS; INFEC; MALILGN; MALUNI; NECRS; NONUNIO; PAIN; REOPOTH; REOPOTHSPF)	Qualitative, nominal	Proportions, frequencies, column and row totals, missing proportion (if any). Listings of other specifications.	х	х	

Table 6.2: Reoperation Tables List

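### A failure judged unrelated to the device counts as event-free in the safety endpoint although the same report tabulates it elsewhere, and no planned analysis links the two

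*Protocol*

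**What the plan says.** The safety endpoint in Protocol section 8.2 reads "Incidence of device-related adverse events by 12 months will be monitored through collection and analyses". Section 13.2 sets the rule for entering the safety data: "Only adverse events/incidents that are considered possibly, probably or definitely related to the device will be captured for this clinical investigation". That sentence is passive and names no assessor. Section 13.1 gives severity grading to the investigator, and section 17 makes the site principal investigator responsible for assessing and reporting events. No independent adjudication is described. Section 7 says that neither "subjects nor investigators are blinded to treatment".

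Section 13 defines an adverse device effect as "any untoward or unintended response to the clinical investigation treatment; and/or a medical response which may have a causal relationship to the treatment". Section 13.3 introduces a list of 25 foreseeable events with "ADEs, SADEs and incidents which may be expected as part of the surgical interventions include".

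Two other sources record failures with no stated attribution condition:

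- **Reoperations.** Protocol section 14: "Reoperations and reason(s) for reoperations will be collected throughout the course of the clinical investigation". SAP section 6.1, Table 6.2, codes them as "Reason(s) for Reoperation (Variable(s): DELUNION; IATRFRAC; IMPBRAK; IMPLFAIL; IMPLOOS; INFEC; MALILGN; MALUNI; NECRS; NONUNIO; PAIN; REOPOTH; REOPOTHSPF", for both interim and final reports.
- **Bone consolidation.** It is assessed at 3, 6 and 12 months until first observed (Protocol section 10.5, note d). It is tabulated in SAP Tables 6.5.1 and 6.6.2, with a listing of the explanations given in Table 6.5.1.

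SAP Table 6.6.3 counts only the first device-related adverse event as an event and censors everyone else. SAP Table 6.1 lists the adverse-event variables, including several marked as not reported, but none for relationship to the device.

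**The concern.** The relatedness judgement is made before an event is recorded, so a negative answer produces no adverse-event record and no grade that could be tabulated. Meanwhile the reoperation and consolidation forms pick up many of the same clinical failures. The final report can therefore show a low device-related incidence next to a reoperation table and a consolidation table that tell a different story, with nothing to show a reader how far the same subjects are involved. In an unblinded single-arm study, the safety figure rests on that judgement.

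**Working it through.** **1. Do the sources cover the same events?** I set the SAP reoperation codes beside the Protocol section 13.3 list.

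| SAP Table 6.2 reason | Section 13.3 entry |
|---|---|
| DELUNION | Delayed union |
| IATRFRAC | Iatrogenic fracture |
| IMPBRAK | Implant breakage (nail, screw) |
| IMPLFAIL | Implant failure (nail, screw) |
| IMPLOOS | Implant loosening (nail, screw) |
| INFEC | Infection (deep, superficial) |
| MALILGN | Axial or rotational malalignment |
| MALUNI | Malunion |
| NECRS | Necrosis |
| NONUNIO | Non-union |
| PAIN | Pain |

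All 11 named reasons match; only the free-text category has no counterpart.

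**2. Follow one subject.** Take a subject reoperated for non-union whose non-union is judged unrelated to the nail.

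- Adverse-event form: none, under section 13.2.
- SAP Table 6.1 incidence: not counted.
- SAP Table 6.6.3: censored at the 12-month visit as a survivor.
- SAP Table 6.2: counted, with the reason non-union.
- SAP Table 6.6.2: recorded as not consolidated, if consolidation is never observed.

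**3. Is there a link?** SAP sections 6.1, 6.6 and 6.7 contain no table that crosses adverse events with reoperation, consolidation or withdrawal by subject. No rule says that a reoperation or a non-consolidated fracture must produce an adverse-event record or a documented decision that none is needed.

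**4. How large could it be?** The documents give no expected event rate, no share judged related, and no target or margin for safety, so there is no plan figure to reproduce. The following is illustration only. With N = 80 planned subjects, p the proportion with a relevant failure and c the share judged related:

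recorded = 80 × p × c; counted event-free = 80 × p × (1 − c)

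| p (assumed) | Subjects with failure | Recorded at c = 25% | c = 50% | c = 75% |
|---|---|---|---|---|
| 5% | 4 | 1 | 2 | 3 |
| 10% | 8 | 2 | 4 | 6 |
| 15% | 12 | 3 | 6 | 9 |
| 20% | 16 | 4 | 8 | 12 |

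At p = 10%, the reported incidence runs from 2/80 = 2.5% to 6/80 = 7.5%, and 8 − 6 = 2 to 8 − 2 = 6 subjects count as event-free. At c = 50% it is 4/80 = 5.0% (exact 95% interval 1.4% to 12.3%) against 8/80 = 10.0% (4.4% to 18.8%).

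**The case against.** The strongest reply is that the endpoint is declared as device-related throughout both documents. An event judged unrelated is event-free for that endpoint by definition, and including the possibly related grade sets a low threshold. That stands, and is why the endpoint itself should stay.

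Several stronger readings are tempting and are not supported:

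- **Section 13.2 contradicts the definition of an adverse device effect.** A reader might infer this because the definition speaks of treatment and section 13.3 of surgical interventions. But the synopsis names the nailing system itself as the treatment, so the passages can be read consistently.
- **The incidence can only be too low.** The filter can only remove events, but under a low threshold an investigator may also attribute fracture or surgical complications to the device. Against truly device-caused incidence, the error can go either way.
- **The failures vanish from the report.** They do not. Reoperations have a table and a Kaplan-Meier analysis (called reoperation in Protocol section 11.3.4 and SAP section 3.1.3, revision surgery in SAP section 6.7.5). Reasons for non-consolidation and for withdrawal are listed, and mortality is analysed.
- **The investigator is stated to make the judgement.** This is inferred from sections 13.1 and 17.

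Two further replies carry some weight. Monitoring under Protocol section 17 checks completed forms against medical records and may find an omitted event, but it is not described as a review of relatedness. The schedule of events puts device-related events and reoperations in one line, which could be read as limiting both; section 14 and SAP Table 6.2 state no such limit.

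**Conclusion.** The point holds as a gap in the planned analysis. A subject with a failure of a kind the protocol lists as a foreseeable device effect can count as event-free in the safety endpoint while that failure is tabulated elsewhere, and no planned analysis connects the two.

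The size is unknown. The 2.5% to 7.5% against 10% rests on an assumed 8 failures in 80 subjects and an assumed 25% to 75% judged related. The safety endpoint has no hypothesis, benchmark or success criterion, so no formal conclusion of the study changes and the primary endpoint is untouched. What is affected is whether a reader can judge the safety figure. The conclusion assumes that reoperations are collected whatever their cause, which section 14 implies by setting no condition.

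**What to change.** Change SAP sections 6.1 and 6.6, using data already planned:

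1. Keep device-related incidence as the endpoint.
2. Add a subject-level reconciliation table. Its rows are subjects with (a) a reoperation for a reason on the section 13.3 list, (b) withdrawal for device removal or an adverse event, or (c) no consolidation recorded at any visit by 12 months. Its columns show whether a device-related event was recorded. Because assessment stops once consolidation is seen, an earlier yes must be carried forward. Show subjects with no 12-month assessment and no earlier yes on a separate line.
3. Report a sensitivity incidence and Kaplan-Meier curve that count all such subjects as events. State the event date for each type (reoperation, withdrawal, or 12-month visit) and a censoring time for subjects without a 12-month visit, which Table 6.6.3 does not give.
4. Report the possibly/probably/definitely grade if the eCRF holds it.

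The sensitivity figure bounds under-attribution only for failures that surface in one of these sources. A foreseeable event that is judged unrelated and leads to none of them would still go unseen.

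A new adverse-event record with a not-related option would close that remainder but should be optional. Enrolment was estimated to start in Q4 2018 and last 32 months, which ends between June and August 2021, and SAP version 3 is dated 23 July 2021. A changed capture rule would come late, need ethics submission (Protocol section 15) and rest largely on retrospective attribution.

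The main fix costs one table, one extra incidence figure and one extra curve. Its downside is a second, less favourable incidence that includes some failures the device did not cause, and it should be labelled so.

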13.3. FORESEEABLE ADE AND SADE

ADEs, SADEs and incidents which may be expected as part of the surgical interventions include:

- Axial malalignment
- Chondromalacia
- Compartment syndrome
- Deep vein thrombosis
- Delayed union
- Fat embolism
- Hematoma
- Iatrogenic fracture
- Implant breakage (nail)
- Implant breakage (screw)
- Implant failure (nail)
- Implant failure (screw)
- Implant loosening (nail)
- Implant loosening (screw)
- Infection (deep)
- Infection (superficial)
- Malunion

- Necrosis
- Non-union
- Pain
- Peripheral nerve injury without specification
- Pressure ulcer
- Pre-tibial fistula
- Pulmonary embolism
- Rotational malalignment

13.4. ADVERSE DEVICE EFFECT/INCIDENT REPORTING AND ANALYSIS

In the event that a SADE, UADE or serious incident occurs, the Investigator is required to notify the Sponsor within 48 hours of being made aware of the event. The Investigator is also required to notify their IRB/EC in accordance with the policies of their local laws and regulations.

14. Reoperations

Reoperations and reason(s) for reoperations will be collected throughout the course of the clinical investigation. A reoperation may include, but not limited to, irrigation and debridement, revision surgery, and/or implant removal.

15. Ethics

This clinical investigation is to be conducted according to International Conference of Harmonisation of Good Clinical Practice (ICH-GCP), applicable regulations, institutional research policies and procedures, Declaration of Helsinki and in compliance with the Clinical Investigation Plan (CIP). Investigators will be trained on the clinical investigation devices and surgical techniques prior to implanting clinical investigation subjects.

This CIP and any amendments will be submitted to a properly constituted independent ethics board, in agreement with local legal prescriptions, for formal approval of the clinical investigation conduct. The decision of the ethics board concerning the conduct of the clinical investigation will be made in writing to the Site Principal Investigator before commencement of this clinical investigation. Clinical investigations shall not begin until the governing regulatory authority has provided full, unconditional approval. Off-label use of the T2 Alpha Tibia Nailing System is not permitted.

